Exclusion criteria (recruitment is not possible if any -at least one- criterion is met)	
 • Relevant comorbidity (with limitations to administer radiotherapy according to protocol) • Prior radiotherapy which results in limitations to administer radiotherapy according to protocol • No large metal implants in vicinity of lesion • Department dose constraints for normal tissue can't be met • Large bony lesions with extensive osseous destruction • Patients symptoms do not correlate with MR findings
Study therapy	
 • Image guided radiotherapy (IGRT) with hypo-fractionated simultaneous integrated boost (IMRT) • GTV1 = MR T2w lesion and ADC $\leq 1200 * 10^{-3}$ mm2/s • GTV2 = MR T2w lesion and ADC \leq median ADC in GTV1 • Each lesion is a CTV, CTV = GTV • PTV=CTV+ margin according to department standards • Dose-fractionation • CTV1: 4 x 5 Gy • CTV2: 4 x 7 Gy
Primary endpoint	Feasibility: Proportion of study participants that complete radiotherapy with $\geq 90\%$ of prescribed dose
Secondary endpoints	
 • Dominant symptom (VAS) • Progression-free survival >6 months • Overall survival

	
• Acute toxicity• Quality of life• Change in ADC from before to end of treatment• Change in ADC from before to 6 month post treatment
Sample size	34 patients has to be included in the study
Study sites	University Hospital Sjaelland, Naestved UKSH Campus Kiel UKSH Campus Luebeck
Time table	Recruitment period: 12 months Start of study: March 2018 End of study: March 2019 Follow-up: minimum \geq 6 months
Financing	Interreg (InnoCan)

3 Background and rationale

Prostate cancer is the major cause of cancer death in men living in developed countries. Large autopsy studies found that patients that presented prostate cancer demonstrated metastatic disease in 35% of cases. Prostate cancer metastases were 90% bone metastases, with 90% of the bone metastases involved the spinal cord, followed by lung (46%), liver (25%) and pleura (21%). Another important pathway is the lymphatic system, which is involved in 9 to 16% of cases, especially at the level of obturator, pre-sacral, internal, and common iliac arteries, and sometimes even the extra-regional para-aortic chains (1).

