- age ≥ 18 years
- Legal capacity, patient is able to understand the nature, significance and consequences of the trial
- Written informed consent

Exclusion criteria:

- Relevant comorbidity (with limitations to administer radiotherapy according to protocol)
- Prior radiotherapy which results in limitations to administer radiotherapy according to protocol
- No large metal implants in vicinity of lesion
- Department dose constraints for normal tissue can't be met
- Large bony lesions with extensive osseous destruction (e.g. vertebral body)
- Patients symptoms do not correlate with MR findings

7 Risks and toxicities

Patients participating in this study will have standard radiotherapy. Consequently, the participating patients face known risks and toxicities following high dose radiotherapy. Patients participating in this study are offered a higher than normal radiation dose to their dominant lesion, but treatment plans will adhere to department standard dose constraints for all organs at risk in order to avoid excessive risks and toxicities.

8 Registration

The consecutive cohort of HRPC patients will be screened for eligibility according to the inclusion criteria's in this protocol. Estimated median survival for patients to be included should preferably be based on the updated model in (6) (see appendix 1). Before inclusion, patient clinical routine blood lab and radiology results should be reviewed. Available clinical routine diagnostic imaging and lab results may be used to calculate the expected median survival for patients using the model in (6) (see appendix 1). (6)Eligible patients will be informed about the study. After given informed consent, patients may be included in the

study. All patients included in the study receive a patient identification number (PID). The PID is composed of the site number and the running patient number (starting with P01, P02,.. ect.).

Site	SiteID
Naestved, Denmark	C1
Kiel, Germany	C2
Lübeck, Germany	C3

For **pseudonymous** registration and recording of all protocol data, the department of oncology, Naestved, will be make an electronic web interface (Easytrial) available for participating sites.

9 Systemic therapy

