10.1 General remarks

The primary endpoint is feasibility. The secondary endpoints are duration of relief from local symptoms, i.e. local symptom progression free survival (LPFS), overall survival, treatment toxicity (RTOG/CTCAE 4.0), Quality of life (EORTC-QLQ-C30 and EPIC26), and change in ADC as surrogate marker of response (21-25). Patients are scheduled for protocol specific follow-up visits at 1, 3, 6 months after end of radiotherapy. Additional MRI (T2w and DWI) will be performed at 1 and 6 months after end of radiotherapy or in case of progression of the dominant symptom.

Preferred technique is hypo-fractionated with high precision radiotherapy (radiosurgery or stereotactic radiotherapy) with few (1 to 5) fractions and ablative total dose. Daily IGRT is mandatory for hypo-fractionated regimens. For the treatment of thoracic lesions and metastases in the upper abdomen, techniques for motion compensation (e.g. breath-hold- or gating techniques) should be used, if available. In specific situations (e.g. spinal metastases with involvement of the spinal canal or cord compression or metastases with infiltration of hollow organs), however, lower doses of radiotherapy may be necessary for adherence of dose constraints or to avoid radiation-induced complications such as perforation. In these cases, moderately hypo-fractionated or even conventionally fractionated regimens should be used. The total dose should exceed at least a dose equivalent to 50Gy in conventional fractionation.

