10.4 Dose specification

The dose will be prescribed as 95%-PTV-coverage. The favorite technique is ablative radiosurgery or hypo-fractionated stereotactic radiotherapy if available, otherwise VMAT or IMRT is allowed. Recommended treatment regime

Technique	Dose and fractionation regimens
Hypo-fractionated regime	PTV1: 4F x 5Gy, total dose 20Gy PTV2: 4F x 7Gy, total dose 28Gy

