16.1 Case number

The objective of this study is to investigate the feasibility of applying hypo-fractionated radiotherapy to treat a dominant symptomatic lesion in patients with HRPC. The hypothesis is that at least 90% of the recruited patients complete combined systemic and local treatment with at least 90% of scheduled radiation dose administered. We use a two-sided one-sample proportion score test to compare the proportion of feasible cases to a reference value of 90%. We want to detect any difference with statistical significance of 5% and a power of 80% for not overlooking a true proportion non-feasible of 70%. The necessary sample size is estimated to 24 cases. Drop-out may happen either due to exclusion, or because patients withdraw their consent for participation. For patients with poor prognosis a realistic drop-out rate is estimated to be 30%, which implicated that **34 patients** must be included in the study to reach significance.

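### Section 10.1's floor of more than 50 Gy equivalent names no volume or scope and conflicts with the protocol's own whole-lesion dose of 4 x 5 Gy

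*Protocol*

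**What the plan says.** Several sections of the protocol describe one regimen. The synopsis lists 4 x 5 Gy to the lesion and 4 x 7 Gy to its most aggressive part as the study therapy. Section 3 states the same doses as the aim. Section 10.3 wants all four fractions delivered within two weeks of the start. The table in Section 10.4 has a single row, giving PTV1 "4F x 5Gy, total dose 20Gy" and PTV2 28 Gy in four fractions, under the label "Recommended treatment regime".

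Section 10.1 (General remarks) reads differently. It prefers one to five fractions with an ablative total dose. For lesions that reach the spinal canal, compress the cord or infiltrate hollow organs, it says that "lower doses of radiotherapy may be necessary for adherence of dose constraints", or to avoid complications such as perforation. In these cases "moderately hypo-fractionated or even conventionally fractionated regimens should be used". The paragraph then ends: "The total dose should exceed at least a dose equivalent to 50Gy in conventional fractionation". No volume, alpha/beta, fraction size or number of fractions accompanies that sentence.

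The primary endpoint in the synopsis is the "Proportion of study participants that complete radiotherapy with" at least 90% of the prescribed dose. Section 16.1 words the criterion as "at least 90% of scheduled radiation dose administered".

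**The concern.** The floor can be read as applying to all study radiotherapy or only to the special situations that precede it, and it fits the whole-lesion dose under neither reading. In the first case the protocol's own PTV1 prescription breaches it. In the second, patients singled out because tissue tolerance is tight would receive a higher whole-lesion equivalent than everyone else.

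Two things are at stake. The first is safety: these are lesions near the cord or in hollow organs, and the sentence pushes the dose upward. Such patients are foreseeable, since Section 3 names urinary retention, rectal obstruction and bleeding as possible dominant symptoms. The second is what counts as study therapy. The trial asks whether a specific short hypofractionated regimen can be delivered. If Section 10.1 also admits long courses, the protocol should say whether completing one of them answers that question. The same uncertainty affects the exclusion criteria on comorbidity and prior radiotherapy, which refer to giving radiotherapy as the protocol specifies.

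**Working it through.** **Inputs.** PTV1: 4 fractions of 5 Gy, and 4 x 5 = 20 Gy as stated. PTV2: 4 fractions of 7 Gy, and 4 x 7 = 28 Gy as stated (both Section 10.4). Floor: more than 50 Gy in conventional fractionation, taken as 2-Gy fractions (Section 10.1). Alpha/beta (*ab*): not given in the protocol, so it is an assumption, shown at 1.5, 3 and 10 Gy.

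**Formula.** For total dose D in fractions of size d, the linear-quadratic equivalent in 2-Gy fractions is EQD2 = D(d + ab)/(2 + ab).

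**Whole lesion, PTV1.** EQD2 = 20(5 + ab)/(2 + ab). To exceed 50 Gy would require 100 + 20ab > 100 + 50ab, which is impossible for any positive ab. The conflict therefore does not depend on the assumed value.

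**Boost, PTV2.** EQD2 = 28(7 + ab)/(2 + ab). To exceed 50 Gy requires 196 + 28ab > 100 + 50ab, so 96 > 22ab, or ab < 4.36.

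| ab (assumed) | PTV1, 20 Gy in 4 | PTV2, 28 Gy in 4 | 50 Gy divided by PTV1 |
|---|---|---|---|
| 1.5 | 37.1 Gy | 68.0 Gy | 1.35 |
| 3 | 32.0 Gy | 56.0 Gy | 1.56 |
| 10 | 25.0 Gy | 39.7 Gy | 2.00 |

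**What the floor implies for the other fractionations.**

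- With 2-Gy fractions, 25 give exactly 50 Gy, which does not exceed it, so 26 are needed (52 Gy).
- With 3-Gy fractions, each contributes 3(3 + ab)/(2 + ab) = 3.86, 3.60 or 3.25 Gy at ab 1.5, 3 or 10. The fewest that exceed 50 Gy are 13 (50.1 Gy), 14 (50.4 Gy) and 16 (52.0 Gy).
- At five fractions per week, two weeks hold 10 fractions. Neither course fits, and neither is a four-fraction treatment.

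**Dose criterion under the stated regimen.** 90% of 20 Gy is 18.0 Gy and 90% of 28 Gy is 25.2 Gy. For a course above 50 Gy, the 90% mark lies above 45 Gy. The planned sample size depends on neither figure.

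**The case against.** The best defence is that the floor concerns the peak dose. In Section 10.1, lower doses may be meant in contrast to the ablative dose mentioned earlier in the paragraph, not to PTV1. The paragraph would then say: ablative where possible, otherwise fractionated and lower, but still above 50 Gy equivalent. With the boost as comparator (68 or 56 Gy at alpha/beta 1.5 or 3), a dose just above 50 Gy is indeed lower. This shows that a coherent reading exists, but Section 10.1 does not state it, and it fails once alpha/beta exceeds about 4.4. A site would have to supply both the volume and the alpha/beta.

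Some stronger inferences are tempting, and the defence is right to reject them:

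- *The endpoint has two different denominators.* A reader might infer this from prescribed in the synopsis and scheduled in Section 16.1. These are ordinary synonyms, and most of the protocol points to one four-fraction regimen. Only the label "Recommended treatment regime" and the allowance in Section 10.1 loosen it.
- *Section 10.1 contradicts the exclusion criterion "Department dose constraints for normal tissue can't be met".* The two can stand together: if a changed fractionation meets the constraints, the patient is not excluded.
- *The result is biased by a known amount.* One patient is 1/24 = 4.2 or 1/34 = 2.9 percentage points, but the protocol gives no count of affected patients, so this measures no effect.
- *Sites cannot know what to give.* This goes too far. Section 10.1 gives a class of fractionation and a floor, and Section 10.5 applies institutional constraints.

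It is also fair that the handling of modified regimens in the analysis may be set out in a statistical analysis plan. A rule on the dose to be delivered belongs in the protocol.

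**Conclusion.** The point holds as a conflict over dose and scope within the protocol. The 50 Gy sentence cannot be satisfied by the whole-lesion prescription at any positive alpha/beta, and the shortfall is 13 to 25 Gy over the assumed range (50 minus 37.1, and 50 minus 25.0). Confined to the special situations, it asks for 1.35 to 2.0 times the standard whole-lesion equivalent where restraint was intended, through courses of 13 to 26 fractions that lie outside the Section 10.3 schedule. These figures rest on the linear-quadratic model and on conventional meaning 2 Gy per fraction. Only the sizes, not the existence of the conflict, depend on alpha/beta.

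The consequence for the primary endpoint is secondary and conditional. A reader might infer that patients completing another regimen are wrongly counted as successes. That follows only if such regimens are outside the study therapy, which the protocol leaves unsettled. The sample size is unaffected.

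**What to change.** 1. In Section 10.1, delete the 50 Gy sentence, or confine it explicitly to a named volume and state the alpha/beta used for the equivalence.
2. In the same section, state whether moderately hypofractionated and conventional courses are study therapy. If they are, give the dose, fraction number and time limit, since Section 10.3 covers only four fractions.
3. As a secondary change, because the trial tests the 4 x 5/4 x 7 Gy regimen, define the 90% criterion in the synopsis and Section 16.1 against 20 Gy to PTV1 and 28 Gy to PTV2, and report patients given another regimen separately.

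The first two changes cost only protocol wording. The third is more than wording: if patients treated as Section 10.1 directs no longer count as completers, the quantity estimated changes and the feasibility proportion may be lower, by an amount the protocol does not allow to be estimated. The result could be sensitive to this. With 24 evaluable patients the standard error under 90% is sqrt(0.9 x 0.1/24) = 0.0612, so the score test rejects on the low side below 0.90 - 1.96 x 0.0612 = 0.78, that is at 18 or fewer completers, against 21.6 expected. Moving three or four patients could change the conclusion, so the definition should be settled before outcomes are known.

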10.2 Treatment planning

3D planning is mandatory. Type of treatment technique (e.g. 3D-IMRT, VMAT or SBRT) is the decision of the radiation oncologist. The reference MR scan (see appendix 2) must be co-registered to the planning CT and the target volumes defined on MR transferred to the planning CT for dose planning.

10.3 Target volumes

Patients included in the study will be subjected to a protocol-specific MRI examination (see MR sequence and example of target delineation in appendix 19-20). A radiologist will read the MRI scan to validate correspondence between MR lesion and the patients dominating symptoms. In case of more than one lesion, decision on priority of target volumes will be made by the radiation oncologist based on clinical expertise. An ADC map will be calculated for the lesion using the DWI sequences. A cutoff ADC value of less than 1200×10^{-6} mm²/s in combination with a T2w image will be used to predict the MR lesion (GTV1) (26). The most aggressive part of the lesion (GTV2) will be defined using ADC of less than or equal to a cutoff value calculated as the median ADC value for the GTV1 (25). Notice that GTV2 need not to be one coherent volume, but may consist of several sub-volumes.

For the definition of target volumes, the following aspects should be considered: The clinical target volume (CTV) is the visible macroscopic tumor (GTV). The safety margin for the planning target volume (PTV) should be according to the department standard, and depending on the radiation technique used. The margin for the PTV2 for CTV2 may be chosen to be smaller than for PTV1 as this volume is enclosed in the CTV1, which receives a dose of 4 x 5Gy already.. For the treatment of breathing-dependent lesions (upper abdomen), treatment techniques with motion compensation (e.g. breath-hold or gating) should be used. All four fractions of the treatment should be given within two weeks of starting the radiotherapy.

10.4 Dose specification

The dose will be prescribed as 95%-PTV-coverage. The favorite technique is ablative radiosurgery or hypo-fractionated stereotactic radiotherapy if available, otherwise VMAT or IMRT is allowed. Recommended treatment regime

Technique	Dose and fractionation regimens
Hypo-fractionated regime	PTV1: 4F x 5Gy, total dose 20Gy PTV2: 4F x 7Gy, total dose 28Gy

10.5 Organs at risk

Organs at risk will be contoured if they are (at least partially) visible on transversal CT-slices on which the PTV is contoured or if the distance to PTVs is less 1 cm than crano-caudal direction. Organs at risk are:

- Spinal cord, brain stem
- Optic nerves and optic chiasm

- eyes
- parotid glands
- lungs
- heart
- esophagus
- liver
- kidneys
- bladder
- rectum

Dose constraints to OARs can be used according to the institutional standard. Doses to OARs (sum plan of all relevant PTVs) will be documented.

Quality assurance procedures will be performed according to the institutional standard. Each participating institution will provide a SOP for quality assurance.

10.6 Start of radiotherapy

Radiotherapy should be started within three weeks after inclusion of the patient in the study.

11 Trial Procedures and Assessment

11.1 Specific diagnostic procedures

A complete staging according to current guidelines with adequate imaging is required. . The available data should give sufficient information about:

- Number of visible metastatic lesions
- location of each lesion (e.g. lung metastasis in left lower lobe, osseous metastases in os sacrum)
- Size of each lesion

Additional specific work-up is not required.

11.2 Baseline examination

A baseline diagnostic MR examination corresponding to dominant symptom must be performed according to trial specifications in appendix 2. The MR images must be co-registered to imaging necessary for radiotherapy planning (CT).

Baseline examination includes:

- Review of medical history inclusive previous anti-cancer treatment
- Review of clinical routine blood and radiology results
- Review of concomitant medication, analgesia, opioids, current systemic anti-cancer treatment
- Tumor staging, grading, classification, localizations, sizes

- Physical examination (incl. height, weight)
- ECOG performance status
- Baseline dominant symptom (VAS score)
- Baseline acute toxicity RTOG/CTCAE v.4.03 scores
- Quality of life (EORTC-QLQ C30)

11.3 End of radiotherapy

At end of radiotherapy, the following must be documented:

- Review of concomitant medication, analgesia, opioids, current systemic anti-cancer treatment
- Review of clinical routine blood results and radiology
- Dominant symptom score (VAS score)
- Acute toxicity (NCI-CTCAE v4.03 score)
- Performance status (ECOG)
- Assessment of AE/SAEs

Details of actually applied treatment are to be documented throughout and to be entered into the CRF at the end of treatment:

- Radiotherapy techniques uses
- Volumes, fractions, doses applied, dose constraint compliance for all organs at risk
- Cumulative doses to target volumes, any boosts

11.4 Follow-up visits

Protocol visits are required at registration for the trial and at end of radiotherapy and at 1,3 and 6 months after end of treatment (see flowchart in appendix 3). At this time, the following examination will be performed:

- Review of concomitant medication, analgesia, opioids, current systemic anti-cancer treatment
- Review of clinical routine blood and radiology results
- Dominant symptom score (VAS)
- Acute toxicities of radiotherapy , RTOG/NCI score
- Quality of life (EORTC-QLQ C30) (only at 6 months)
- ECOG performance status
- Assessment of AE/SAE

All later visits are scheduled according to standard guidelines and institutional procedures.

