The aim of the present study will be to conduct a feasibility study of a new short palliative radiotherapy regime that apply to patients with metastatic HRPC patients presenting with a dominating debilitating symptom and an expected reasonable survival. The dominant symptom can be such as pain, urinary retention, chronic rectal obstruction, bleeding etc., caused by localized progression of the patient's metastatic prostate cancer. This new approach will apply magnetic resonance imaging (MRI) to verify correspondence between the progressing HRPC lesion (DSL =the dominant symptomatic lesion) and the patients corresponding dominant symptom. Diffusion weighted MR imaging (DWI) will apply to identify both the lesion and the most aggressive part of the lesion. The symptomatic lesions will be treated using precision radiotherapy (IGRT+IMRT/VMAT or SBRT/SRS if available) with a dose of 4 x 5 Gy, while for the most aggressive part of the lesion the dose will be escalated to 4 x 7 Gy using a simultaneous integrated boost (SIB) technique.

4 Objective

This prospective study will evaluate the feasibility as the primary endpoint. Secondary endpoints are visual analog score (VAS) of the dominating symptom, symptom progression free survival, evaluation of radiation induced acute toxicity, the influence on quality of life, the progression free survival and change in volume and ADC statistics from baseline as surrogate marker of local response to radiotherapy. The study will analyze patient characteristics, relevant comorbidities and tumor related factors correlation to outcomes. Based on the results of this study, a prospective randomized phase II/III dose escalation study may suggested.

5 Study design and participating centers

This is an international, multi-center single arm prospective feasibility study. Participating sites are:

1. University Hospital Sjaelland, Naestved, Department of Oncology
2. UKSH Campus Kiel, Department of Radiation Oncology
3. UKSH Campus Luebeck, Department of Radiation Oncology

6 Inclusion and exclusion criteria

Patients can be included in the study if they fulfill all of the following inclusion criteria and none of the following exclusion criteria.

Inclusion criteria:

- Patients with hormone refractory biopsy proven prostate cancer (HRPC)
- Presenting with a dominating debilitating symptom
- Expected median survival of 3-12 months (6)
- Focal irradiation of lesion is feasible
- Systemic therapy according to guidelines

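### Quality of life has a single post-treatment assessment, at 6 months, in men selected for an expected median survival of 3 to 12 months

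*Protocol*

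**What the plan says.** Section 4 of the protocol includes QoL among the secondary endpoints: "evaluation of radiation induced acute toxicity, the influence on quality of life, the progression free survival". The synopsis lists it too, and Section 10.1 names two instruments: "Quality of life (EORTC-QLQ-C30 and EPIC26".

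The schedule is as follows.

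- Section 11.2, baseline: "Quality of life (EORTC-QLQ C30".
- Section 11.3, end of radiotherapy: no QoL item. The list does include "Dominant symptom score (VAS score", toxicity and ECOG.
- Section 11.4, follow-up: "Quality of life (EORTC-QLQ C30) (only at 6 months".
- Appendix 4, flowchart: the QoL row is marked at baseline and 6 months only, and names no instrument. VAS, toxicity and ECOG are marked at baseline, after radiotherapy, and at 1, 3 and 6 months.

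The 1- and 3-month visits are part of the protocol in any case: "Protocol visits are required at registration for the trial and at end of radiotherapy and at 1,3 and 6 months after end of treatment". The eligibility criterion in Section 6 is "Expected median survival of 3-12 months (6".

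**The concern.** For men near the low end of the eligible range, the only post-treatment QoL assessment falls after the time by which half are expected to have died. A change from baseline needs both forms, so it exists only for men who reach 6 months, are still on study and can answer. Those who die, withdraw or are taken off study contribute a baseline value and nothing else. Section 17.2 makes disease progression a reason to end participation, and no QoL form is planned at progression or withdrawal.

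A secondary question about the influence of a four-fraction palliative course on QoL would then be answered in a subset defined by the patients' later course, with no global QoL reading before 6 months. A statistical analysis plan can describe this loss but cannot recover questionnaires that were never given.

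**Working it through.** **The plan's own figure.** The protocol states no sample size or expected attrition for QoL, so the denominator is the 34 patients of Section 16.1. That figure reproduces within rounding: n = [(1.96·√(0.9·0.1) + 0.842·√(0.7·0.3)) / 0.2]² = 23.7, so 24; and 24 / (1 − 0.30) = 34.3, stated as 34.

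**Inputs.**
- Expected median survival: 3 to 12 months (Section 6).
- Visits at 1, 3 and 6 months after the end of treatment (Section 11.4).
- Delay before radiotherapy: "Radiotherapy should be started within three weeks after inclusion of the patient in the study" (Section 10.6).
- Duration of radiotherapy: up to two weeks (Section 10.3).

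**Assumption.** The protocol gives a range of medians but no curve. I assume exponential survival, S(t) = 0.5^(t/median), with all 34 patients contributing a baseline form.

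**Share alive, clock from end of radiotherapy (number of 34):**

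| Visit | Median 3 months | Median 6 months | Median 12 months |
|---|---|---|---|
| 1 month | 79% (27.0) | 89% (30.3) | 94% (32.1) |
| 3 months | 50% (17.0) | 71% (24.0) | 84% (28.6) |
| 6 months | 25% (8.5) | 50% (17.0) | 71% (24.0) |

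For example, at 6 months with a 3-month median, 0.5^(6/3) = 0.25 and 34 × 0.25 = 8.5.

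**Clock from inclusion.** Three weeks to start plus two weeks of treatment is 35 days, or 35/30.44 = 1.15 months. The 6-month visit then falls up to 7.15 months after inclusion, and the shares alive are 19%, 44% and 66% (6.5, 14.9 and 22.5 of 34).

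**Spread of medians.** If the medians were spread evenly over 3 to 12 months, 54% (18.5 of 34) would be alive at the 6-month visit counted from the end of radiotherapy, and 49% (16.6) counted from inclusion.

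**Shape of the curve.** Weibull shapes 1.5 and 2, counted from the end of radiotherapy, give 14% and 6% alive at 6 months for a 3-month median, and 78% and 84% for a 12-month median. For a 6-month median the share is 50% whatever the shape.

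All these figures are upper limits on the number of paired forms, because they count deaths only.

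**EPIC-26.** Section 10.1 names the QLQ-C30 and EPIC-26. Sections 11.2 and 11.4 list the QLQ-C30 alone, Section 11.3 lists no QoL instrument, and the flowchart row is unnamed.

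**The case against.** The timing is consistent across Sections 11.2 to 11.4 and the flowchart, so it is a choice and not a slip. The protocol describes these patients as typically frail, and sparing them forms is a reasonable aim. QoL is one of several secondary endpoints in a small single-arm feasibility study whose primary endpoint is completion of the radiation dose. All of that stands, and it is why this is an improvement and not a fault that endangers the trial.

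Four stronger readings are tempting, and the documents do not support them.

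- A reader might infer that QoL will be answered only by the patients who fare best. That fits mainly the low end of the range. With a 12-month median about 71% are still alive, and the protocol does not give the distribution of predicted medians.
- A reader might infer that the period of palliative benefit is missed altogether. It is not: the dominant-symptom VAS, toxicity, ECOG, analgesic and opioid use and adverse events are recorded at the end of radiotherapy and at 1 and 3 months. What is missing early is global QoL.
- A reader might infer that the result must be biased towards benefit. Selection by survival favours fitter men, but there is no control arm, and the 6-month value also reflects six months of incurable disease and concurrent systemic therapy. That could hide an early gain.
- A reader might infer that EPIC-26 will have no data. The flowchart's QoL row could cover both instruments, so the text supports only that EPIC-26 is not scheduled by name.

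Naming a main QoL time point and reporting how many are alive and answering can be left to the statistical analysis plan, so their absence here is no finding.

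**Conclusion.** The point holds as a design weakness in a secondary endpoint. The only post-treatment QoL form is due when about a quarter to 71% of the men are expected to be alive, under exponential survival from the end of radiotherapy and before any other loss. The same model gives 79-94% at 1 month and 50-84% at 3 months. The exact shares depend on the assumed curve, the starting clock and the mix of medians. The ordering does not: fewer patients can answer at 6 months than at the visits already held earlier. How far, and in which direction, the observed change would be distorted cannot be settled from the protocol. The EPIC-26 mismatch is a separate, minor inconsistency.

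**What to change.** In Section 11.4 and the Appendix 4 flowchart, replace the restriction to 6 months with the QLQ-C30 at the existing 1-, 3- and 6-month visits. This needs no new visit. The cost is a wording change and one extra questionnaire at each of two visits, which is a modest burden for frail patients.

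Separately, reconcile Section 10.1 with Sections 11.2 to 11.4: either list EPIC-26 by name at baseline and the chosen follow-up visits, and name the instruments in the flowchart row, or delete it from Section 10.1. Deleting it costs nothing; scheduling it adds a second form at each of those visits.
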